5 IMPLEMENTATION OF THE STUDY

This study consists of the following study periods:

- Inclusion and randomization visit: inclusion and randomization during hospitalization
- Every day visit during hospitalization (until day 28, discharge or death): prospective collection of the events occurring during the index hospitalization until day 28, discharge or death
- Visit or phone call (for patients discharged from the hospital) at day 28 (± 4 days): collection of the events occurred since hospital discharge

5.1 Inclusion and randomization visit

This visit will take place within the framework of hospitalization for COVID-19.

In each 12 hospital of AP-HP, patients with a SARS-CoV-2 infection can be enrolled in any “non-ICU” department. In practice, considering the evolving situation in each hospital in Paris, patients could be included in any medical department: cardiology, infectious diseases, internal medicine, nephrology, endocrinology, neurology, pneumology. A coordinating investigator for each center will be designed to list all the co-investigators who can enroll patients.

After verification criteria for inclusion and non-inclusion, the investigator presents to the patient the ACORES-2 study and will be given time for reflection in order to obtain his participation agreement.

If the patient agrees to participate, the investigator will collect the written informed consent.

The patient will be included during the hospitalization in a study participating center.

Whose consent must be obtained	Who informs the individuals and collects their consent	At what point the individuals are informed	At what point the consent is obtained
The patient	Investigator (physician)	V0 visit (in-hospital admission)	After a reflection period of 6 hours at the latest after the patients' information

During this visit, the following data will be collected and some procedures and treatments will be carried out:

- Informed consent collection
- Inclusion/exclusion criteria review
- Demographic characteristics: date of birth, gender, height, and weight, blood group
- CV risk factors: smoking habits, diabetes, hypertension, dyslipidemia, family CAD, presence or not of a renal insufficiency (creatinine clearance ≤ 60 ml/min)
- Medical and cardiovascular history: heart failure (with either preserved or reduced left ventricular ejection fraction), coronary artery disease, cerebrovascular disease, cardiomyopathy, valvular heart disease
- Other comorbidities: chronic lung disease, cancer, immunodeficiency, HIV
- Concomitant treatments at inclusion: mineralocorticoid receptor agonist, sacubitril, beta-blockers, calcium channel blockers, thiazides, loop diuretics, alpha-blockers, central acting agents, corticosteroids, nonsteroidal anti-inflammatory drugs
- Vital signs: pulse, blood pressure, respiratory rate, oxygen saturation, temperature
- Clinical status on a seven-category ordinary scale, as defined above
- Date of beginning of symptoms
- Symptoms compatible with SARS-CoV-2 infection: fever, cough, dyspnea, anosmia, ageusia, ocular congestion, myalgia, sputum production, anorexia, fatigue, headache, sore throat, rhinorrhea, digestive symptoms (diarrhea, nausea, vomiting)
- Complete physical examination
- Biology: complete blood count, creatinine, blood urea nitrogen, potassium, sodium, bicarbonate, alanine/aspartate aminotransferase, bilirubin, albumin, lactate dehydrogenase, prothrombin time, activated partial thromboplastin time, D-dimers, troponin I us, creatine kinase, natriuretic peptides (BNP or Nt-proBNP), C-reactive protein, procalcitonin, ferritin, arterial blood gas with lactate
- Blood group and rhesus will be determined at inclusion if not performed earlier. Data will be collected in the CRF. Indeed, it has been reported in 2,173 Chinese patients with COVID-19 that blood group A was associated with a higher risk for acquiring COVID-19 compared with non-A blood groups, whereas blood group O was associated with a lower risk for the infection compared with non-O blood groups. this observation was reported in a preprint article without peer-review and further investigation are of the relationship between the ABO blood group and the COVID-19

susceptibility is important (Zhao J, Yang Y, Huang H, Li D, Gu D, Lu X, et al. Relationship between the ABO Blood Group and the COVID-19 Susceptibility. medRxiv. 27 mars 2020;2020.03.11.20031096.)

Any arterial puncture for collecting arterial blood gas and/or lactate should be performed after topical anesthesia with lidocaine 5% cream (EMLA)™

5.2 Every day visit in hospitalization until day 28, discharge or death

The patients will have a daily visit during hospitalization until day 28, discharge or death. All the events occurring during hospitalization will be collected prospectively, as well as the date of onset:

- Clinical status on a seven-category ordinary scale (as defined above) each day
- Hospital discharge
- Cross-over
- Cardiovascular death
- Non cardiovascular death and cause
- myocardial infarction
- Myocarditis
- Stroke
- Heart failure; presence of congestive signs, IV use of diuretics
- Acute kidney injury, as defined in the KDIGO (Kidney Disease: Improving Global Outcomes) guidelines (45): increase in serum creatinine $\geq 26.5 \mu\text{mol/L}$ within 48h or ≥ 1.5 times baseline within the last 7 days or urine output $< 0,5 \text{ ml/kg/h}$ for 6 hours
- ICU admission (and date of discharge if happens)
- Oxygen requirement: date of beginning and cessation
- Mechanical ventilation (non-invasive or invasive): date of beginning and cessation
- Acute respiratory distress syndrome, as define by the Berlin criteria (46): acute lung injury ≤ 1 week, bilateral opacities consistent on chest imaging not fully explained by other lung pathology, heart failure or volume overload, $\text{PaO}_2/\text{FiO}_2$ ratio $\leq 300\text{mmHg}$ with a minimum of 5 cm H_2O PEEP (or CPAP)
- Shock requiring vasopressors
- Extracorporeal membrane oxygenation (ECMO): date of beginning and cessation
- Renal replacement therapy: date of beginning and cessation
- Biology: as mentioned at 5.1, according to the physician's decision

5.3 End of study visit (visit or phone call at day 28 \pm 4 days)

- All patients still hospitalized at day 28, will have a visit with an events collection as mentioned at 5.2.
- All survivors' patients already discharged from hospital will have a phone call by an investigator (physician) at day 28 (± 4 days) to collect the events occurred since discharge from hospital:
 - Clinical status on a seven-category ordinary scale (as defined above)
 - New hospitalization in a non-ICU
 - Cardiovascular death

- Non cardiovascular death and cause
- Myocardial infarction
- Myocarditis
- Stroke
- Heart failure; presence of congestive signs, IV use of diuretics
- Acute kidney injury, as defined in the KDIGO guidelines
- ICU admission
- Oxygen requirement: date of beginning and cessation
- Mechanical ventilation (non-invasive or invasive): date of beginning and cessation
- Acute respiratory distress syndrome, as define by the Berlin criteria
- Shock requiring vasopressors
- Extracorporeal membrane oxygenation (ECMO): date of beginning and cessation
- Renal replacement therapy: date of beginning and cessation

5.4 Expected length of participation and description of the chronology and duration of the study.

Duration of enrolment period:	1 month
The length of participation for participants, of which:	28 days (+/- 4 days)
Maximum period between screening and enrolment:	7 days
Treatment duration:	1 month
Duration of follow-up period:	1 month
Total study duration:	2 months

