12.4.2 Secondary Efficacy Criteria

If a significant difference is found for the main criterion, The secondary criteria will be tested using a hierarchical procedure in the following order:

1. Clinical status as assessed with the seven-category ordinal scale on days 28.
3. Number of days alive free of oxygen.
4. Number of days alive outside hospital during 28 days after randomization.
5. Number of days alive free of intensive-care unit (ICU) admission or mechanical ventilation (invasive or non-invasive) 28 days after randomization.
6. Number of days alive free of mechanical ventilation (invasive or non-invasive) 28 days after randomization.
7. Number of days alive free of ICU admission 28 days after randomization.
8. Rate of all-cause mortality at day 28.
9. Rate of cardiovascular death at day 28.
10. Number of days alive free of acute kidney injury during hospitalization.

Secondary criteria will be compared using Mann-Whitney tests for quantitative variables and ordinal logistic regression to analyze the seven-category ordinal. Chi-square tests for categorical data and Cox survival analysis for time to event. Tests will be performed at a two-sided 5% significant level for one criterion only if a significant difference has been found for the previous criterion in the list.

Differences in medians between groups will be reported with associated 95% CI

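### The data listed in Protocol 5.2 and 5.3 cannot determine AKI-free days in hospital, or hospital-free and ICU-free days for patients readmitted after discharge

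*Protocol*

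**What the plan says.** Protocol 5.2 covers the daily visit and requires: "All the events occurring during hospitalization will be collected prospectively, as well as the date of onset". Section 5 limits this daily collection to the index hospitalization. Within the 5.2 list, ICU admission also carries a discharge date. Oxygen, mechanical ventilation, ECMO and renal replacement therapy each carry start and stop dates, in the form "Oxygen requirement: date of beginning and cessation". AKI is listed by its KDIGO definition with no end date. Section 8.1.6 gives criteria for onset and stage, but none for resolution. Laboratory tests after baseline are listed as "Biology: as mentioned at 5.1, according to the physician's decision".

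Protocol 5.3 has one phone call at day 28 (± 4 days) for patients already discharged. Its list includes "New hospitalization in a non-ICU" and ICU admission, both without dates. Oxygen, ventilation, ECMO and renal replacement in the same list again carry start and stop dates.

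Section 12.4.2 places these day counts in the hierarchical test order: "Number of days alive outside hospital during 28 days after randomization", days free of ICU or ventilation, days free of ICU and, last, "Number of days alive free of acute kidney injury during hospitalization".

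**The concern.** A day count needs the start and the end of each episode. The protocol asks for both where it lists oxygen, ventilation, ECMO and renal replacement, but not for AKI or for stays after discharge, although tested endpoints depend on them. An analysis plan can define how dates are used, but it cannot recover dates that were never collected.

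The hospital and ICU counts run over 28 days from randomization, so time after discharge belongs in them. They also stand before all-cause mortality in the hierarchy. A count that cannot be determined there bears on whether the later criteria are formally tested. Section 2.7 names acute heart failure as a risk of discontinuation and less AKI as a possible benefit. Readmission and AKI duration are therefore outcomes on which the two strategies might differ.

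**Working it through.** The plan states no figure to reproduce. The check compares what each endpoint needs with what is listed, then bounds the count for illustrative patients.

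| Day count in 12.4.2 | Needed | Listed | Determined? |
|---|---|---|---|
| Free of oxygen; free of ventilation | start and stop | start and stop, 5.2 and 5.3 | yes |
| Free of ICU, index stay | admission and discharge | both, 5.2 | yes |
| Free of ICU (alone or with ventilation), after discharge | admission and discharge | neither, 5.3 | no, if admitted |
| Outside hospital | first discharge, plus dates of any readmission | first discharge only | no, if readmitted |
| Free of AKI in hospital | start and end | start only, 5.2 | no, if AKI occurs |

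**Whether other listed items fill the gap.** The seven-category scale is recorded daily in hospital and once at the end. At the day-28 contact it can show that a readmission is ongoing or over, but not when it began or ended. The 5.2 list has no readmission item, and 5.3 carries the 5.2 collection over only to patients still in hospital at day 28. Creatinine during the stay is discretionary, urine output is not a listed data item, and no rule says when AKI ends. Renal replacement dates cover only the most severe AKI.

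**Patient A (assumed): AKI starts on day 5 of a 14-day stay, patient alive.** AKI-free days = 14 − k, where k is the number of AKI days. With no end date, k can be 1 to 10 (days 5 to 14). The count lies between 14 − 10 = 4 and 14 − 1 = 13.

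**Patient B (assumed): discharged on day 10, one undated readmission, alive at day 28.** Days outside hospital = 28 − 10 − L, where L is the number of days readmitted, about 1 to 18. The count lies between 28 − 10 − 18 = 0 and 28 − 10 − 1 = 17. Ignoring the readmission would give 28 − 10 = 18. If that stay was in ICU and there was none before, ICU-free days lie between 28 − 18 = 10 and 28 − 1 = 27.

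**How many patients, as a scale only.** Section 2.3 gives AKI in 6 to 10% of severe COVID-19. Applied to 277 per arm: 277 × 0.06 = 16.6 and 277 × 0.10 = 27.7, about 17 to 28. The documents give no readmission rate. An assumed 5 to 10% would be 277 × 0.05 = 13.9 to 277 × 0.10 = 27.7, about 14 to 28 per arm.

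**The case against.** The strongest reply is that a visit list is not the CRF. Section 11.4.1 says the electronic form will be designed to meet the protocol's data requirements, and those arguably include whatever the endpoints need. Date fields and derivation rules are often settled there or in the analysis plan. Sections 10.3.2.2 and 10.3.2.4 also have rehospitalization, ICU admission and AKI recorded in the CRF as serious adverse events, and have adverse events followed to resolution. This stands to the extent that the dates may in practice be captured. But the CRF is to be built from the protocol's requirements, the protocol sets out dates for the neighbouring items and not for these, and the safety sections do not say that end dates are recorded or feed these endpoints.

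A reader might go further and infer that readmitted patients keep full credit from their first discharge, so that the arm with earlier but less durable discharge is favoured. The documents do not support this. No section says that readmission days are ignored, and the endpoint's own wording points the other way. The 5.3 contact would record that Patient B had been readmitted, which contradicts a score of 18.

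It would also be too strong to say that short and long AKI necessarily score the same, because creatinine separates them where it happens to be measured. Nor are all ICU counts affected, since stays within the index hospitalization are fully dated.

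On consequence, it is fair that AKI-free days stand last in the hierarchy and are tested only if every earlier criterion is significant.

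**Conclusion.** The point holds in limited form. As listed, the data do not determine AKI-free days for patients with AKI in hospital. They also do not determine hospital-free, ICU-free or ICU-or-ventilation-free days for patients admitted again after discharge. These are tested secondary endpoints, so the gap should be closed. The primary endpoint, oxygen-free and ventilation-free days, and ICU days in the index stay are unaffected.

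For one patient the uncertainty can be large: 4 to 13 AKI-free days for Patient A, and 0 to 17 days outside hospital for Patient B. Both patients are illustrations. The patient counts are only a scale: the AKI rate comes from severe disease, while the trial excludes shock and invasively ventilated ARDS at entry, and the readmission rate is assumed. Having AKI or a readmission does not in itself mean being mis-scored. The direction and size of any difference between arms cannot be derived from the documents. The conclusion assumes that the CRF follows the 5.2 and 5.3 lists. If it already holds these dates, only the protocol text needs to be brought into line.

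**What to change.** In 5.3, replace the two undated items with any new hospitalization and any ICU stay since discharge, each with admission and discharge dates. State there or in 12.4.2 that those days are subtracted from the hospital-free and ICU-free counts.

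In 5.2, record the date AKI ends, or record AKI status at each existing daily visit. Define the end by a rule consistent with all the criteria in 8.1.6. A rule on creatinine level alone would not be enough, because 8.1.6 also uses urine output and a rise within 48 hours. The rule should say what is assumed on days without a measurement, since testing is discretionary.

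The cost is a few extra CRF fields and one or two protocol sentences. The daily visit and the day-28 contact already take place, and the contact already asks for start and stop dates of other items.

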3.2 Secondary objectives

- To evaluate the safety of RAS blockers discontinuation on a composite endpoint of major adverse cardiac events defined as the composite of cardiovascular death, myocardial infarction, stroke or acute heart failure at day 28.
- To evaluate the efficacy of RAS blockers discontinuation:
 1. Clinical status as assessed with the seven-category ordinal scale on day 28.
 2. Number of days alive free of oxygen.

3. Number of days alive outside hospital during 28 days after randomization.
4. Number of days alive free of intensive-care unit (ICU) admission or mechanical ventilation (invasive or non-invasive) 28 days after randomization.
5. Number of days alive free of mechanical ventilation (invasive or non-invasive) 28 days after randomization.
6. Number of days alive free of ICU admission 28 days after randomization.
7. Rate of all-cause mortality at day 28.
8. Rate of cardiovascular death at day 28.
9. Number of days alive free of acute kidney injury during hospitalization.

4 **STUDY DESIGN**

4.1 ***Study endpoints***

4.1.1 **Primary endpoint**

The primary endpoint of the study is the time to clinical improvement from day 0 to day 28, defined as an improvement of two points on a seven-category ordinal scale, or live discharge from the hospital (whichever comes first), as recommended by the WHO R&D Blueprint expert group (3).

The seven-category ordinal scale consisted of the following categories:

1. not hospitalized with resumption of normal activities
2. not hospitalized, but unable to resume normal activities
3. hospitalized, not requiring supplemental oxygen
4. hospitalized, requiring supplemental oxygen
5. hospitalized, requiring nasal high-flow oxygen therapy, noninvasive mechanical ventilation, or both
6. hospitalized, requiring ECMO, invasive mechanical ventilation, or both
7. death.

4.1.2 **Secondary endpoints**

1. **Primary safety endpoint:** major adverse cardiac events defined as the composite of cardiovascular death, myocardial infarction, stroke or acute heart failure at day 28.
2. **Key secondary efficacy endpoints:**
 - Clinical status as assessed with the seven-category ordinal scale on days 28.
 - Number of days alive free of oxygen.
 - Number of days alive outside hospital during 28 days after randomization.
 - Number of days alive free of intensive-care unit (ICU) admission or mechanical ventilation (invasive or non-invasive) 28 days after randomization.

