 - Number of days alive free of mechanical ventilation (invasive or non-invasive) 28 days after randomization.
 - Number of days alive free of ICU admission 28 days after randomization.

- Rate of all-cause mortality at day 28.
- Rate of cardiovascular death at day 28.
- Number of days alive free of acute kidney injury during hospitalization.

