4.2.4 Randomization

Randomization will be performed with IWRS (Cleanweb).

[figure not shown]
URC Lariboisière Saint-Louis will be done randomization list according to AP-HP Standard Operating Procedures (SOP).

Patients fulfilling the inclusion criteria and without any exclusion criteria that agree to enter the protocol and have signed the inform consent form during the consultation (inclusion) will be randomized in a 1:1 ratio to:

- Group Discontinuation = discontinuation of RAS blocker therapy until the end of the study which correspond to day 28 (experimental arm). After day 28, RAS blockers could be reintroduced or not, according to the physician decision.
or
- Group Continuation = continuation of RAS blocker therapy (control arm)

The randomization will be stratified on the indication of RAS blockers (heart failure vs. other indication).

Inclusion and randomization will be done the same day.

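### The only post-discharge call may be made from day 24, so for discharged survivors up to 4 of the 28 days can go unobserved for the day-28 safety and secondary endpoints

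*Protocol*

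**What the plan says.** Follow-up runs along two routes.

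- **In hospital.** Section 5.2: "The patients will have a daily visit during hospitalization until day 28, discharge or death". Section 5.3 adds: "All patients still hospitalized at day 28, will have a visit with an events collection as mentioned at 5.2".
- **Discharged survivors.** Section 5.3: they "will have a phone call by an investigator (physician) at day 28 (± 4 days", and the purpose is "to collect the events occurred since discharge from hospital". The ordinal category is recorded at the same call. No other contact after discharge is scheduled.

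The ± 4 days also appears in the summary, the introduction to section 5, and sections 5.4, 5.5, 6.4.1 and 10.3.2.3.

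The endpoints in sections 3.2 and 4.1.2 have a fixed horizon. The primary safety endpoint is "major adverse cardiac events defined as the composite of cardiovascular death, myocardial infarction, stroke or acute heart failure at day 28". Others are "Rate of all-cause mortality at day 28", cardiovascular death and ordinal status at the same day, and day-counts such as "Number of days alive outside hospital during 28 days after randomization". Section 4.2.4 describes the experimental arm as "discontinuation of RAS blocker therapy until the end of the study which correspond to day 28".

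**The concern.** The window for the last contact is symmetric about the endpoint horizon, but only its late half can deliver the endpoint. A call on day 24, 25, 26 or 27 cannot record a death, readmission, cardiovascular event or ordinal category that arises afterwards and up to day 28. It also precedes the end of the assigned strategy.

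The protocol sets this rule itself, and no later analysis document can recover days that nobody observed. The stated comparisons give little room for shorter follow-up. Section 12.5 compares dichotomized safety endpoints by chi-square on proportions, and section 12.4.2 gives the same test for categorical secondary endpoints. Ordinal status on day 28 stands first in the hierarchy of section 12.4.2 and gates every later secondary test. Most discharged patients will be in category 1 or 2, separated by return to normal activities, which can change within days during convalescence. The late half of the window has a milder form of the problem: a category asked on day 32 describes day 32 unless the question refers back to day 28.

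**Working it through.** The plan states no figure on this point, so there is none to reproduce.

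**Inputs from the protocol:** call window 28 ± 4 days (5.3); horizon 28 days (3.2, 4.1.2); 28-day mortality 22% (10.3.2.2); 554 patients, control median 16 days, difference 5 days (12.8).

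**Assumptions:** constant hazard of death; 5% to 25% of deaths between day 24 and day 28 occur after discharge; calls either all on day 24 (worst case) or spread evenly over the window.

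1. **Window.** 28 − 4 = 24 and 28 + 4 = 32. Calls on days 24, 25, 26 and 27 miss 4, 3, 2 and 1 days. The worst case for one patient is 4/28 = 14.3%.
2. **Even spread.** Four of nine allowed days are early, 4/9 = 44%. Their mean shortfall is (4 + 3 + 2 + 1)/4 = 2.5 days. Over all calls that is 4/9 × 2.5 = 1.1 days, or 1.1/28 = 4%.
3. **Endpoints reached by the window.**
   - Affected: MACE, ordinal status, all-cause and cardiovascular mortality, and days alive outside hospital, free of ICU or ventilation, free of ventilation, and free of ICU.
   - Not affected: the primary endpoint, because live discharge is itself the event and every patient on the phone route already has it; and kidney-injury-free days, which are counted only in hospital.
   - Undetermined: oxygen-free days, which state no horizon.
4. **Missed deaths.** Daily hazard h = −ln(1 − 0.22)/28. Mortality at day 24 = 1 − exp(−24h) = 19.2%. The gap to day 28 is 22.0 − 19.2 = 2.8 points, about 16 of 554 patients. That ceiling needs every patient closed on day 24, which daily inpatient visits rule out. With every discharged patient called on day 24:
   - 5% of these deaths after discharge: 0.05 × 2.8 = 0.14 points, 0.8 of 554.
   - 25% after discharge: 0.25 × 2.8 = 0.70 points, 3.9 of 554.
   - With calls spread evenly, multiply by 1.1/4: about 0.2 to 1.1 deaths.
5. **Difference between arms.** With exponential times, the share improved by day 24 is 1 − 2^(−24/m). For m = 16 it is 64.6%, and for m = 11 it is 78.0%. Treating improvement as discharge, 13 points more of the discontinuation arm would be on the phone route if the hypothesis in section 2.1 were true. With equal medians the difference is zero. Improvement overstates discharge, since a patient entering in category 5 can improve by two categories while still in hospital.

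**The case against.** The case for leaving the window alone has substance. It covers only discharged survivors; in-hospital events are recorded daily, with onset dates, up to day 28. The 14.3% is unobserved time for one patient in the worst case, not bias in an endpoint, and on an even spread the average loss is about 4%. The mortality arithmetic gives a handful of deaths at most. Start and stop dates for oxygen, ventilation, ECMO and renal replacement are already collected at the call, so cutting late calls back to day 28 is partly possible now. All of this stands, and it limits the size of the point.

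A reader might draw three stronger conclusions that the documents do not support.

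- **That all day-count endpoints, or all patients, are cut short.** Four of the six day-counts are tied to 28 days, and inpatients are followed to day 28.
- **That the unobserved days are counted as event-free.** No section says so. Section 12.6 plans multiple imputation for missing data in the intention-to-treat analysis. A compliant early call might never be flagged as missing, but that is a possibility and not a stated rule.
- **That the truncation favours one arm.** This requires discharge rates to differ, which is the trial's alternative hypothesis and not a known fact.

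What the objection does not answer is that no further contact closes the gap, and that the chi-square comparisons of proportions at day 28 presuppose follow-up to day 28.

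**Conclusion.** The point holds for survivors already discharged. A compliant call on days 24 to 27 leaves 1 to 4 of 28 days unobserved for the primary safety endpoint, the first endpoint in the secondary hierarchy, both mortality endpoints and four day-counts. The 4-day maximum follows from the text alone. The 44% share of early calls rests on an even spread that the protocol does not state.

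The number of missed deaths is probably small: about 1 to 4 of 554 with every discharged patient called on day 24, given a constant hazard and the assumed 5% to 25% share of deaths after discharge. The documents give no rates of cardiovascular events or readmission after discharge, so the loss on MACE and the day-counts cannot be sized. Any imbalance between arms is conditional on different discharge rates. The primary efficacy result is not at risk. The point deserves correction because the loss is avoidable and falls on the main safety comparison.

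**What to change.** Set the call window for discharged survivors to day 28 to day 32, never before day 28. Have the caller ask for vital status, ordinal category and the dates of all events as of day 28, so that information from later calls is cut back to day 28. Section 5.3 should ask explicitly for onset dates of every event, including readmission and ICU admission, as section 5.2 does for inpatients.

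Align every place that carries the ± 4 days: the design and duration rows of the summary, the introduction to section 5, and sections 5.3, 5.4, 5.5, 6.4.1 and 10.3.2.3. Changing only some of them would create new inconsistencies.

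Early closure falls from at most 4 days to none. The cost is a narrower calling window, five days instead of nine, with the same number of calls and the same latest date.
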